4 DEFINITIONS AND DERIVATIONS

Baseline: Baseline is defined as the latest non missing assessment prior to the administration of the first dose of the study drug, unless otherwise specified. If the assessment occurs on the same date as the dose administration, then the time of assessment should be compared to the time of dose administration.

Change from Baseline: The change from baseline values will be calculated as post-baseline value minus the baseline value.

Change from Baseline=Post baseline value - Baseline value

Treatment Emergent Adverse Event (TEAE): A treatment-emergent adverse event (TEAE) is any AEs that begin or worsen after the first dose of the study drug administration in the Treatment Phase.

4.1 Endpoint Derivations

Pain Intensity:

Participants will assess their current pain intensity using an 11-point (0: No Pain to 10: Worst possible pain) Numerical Rating Scale (NRS). Each Participant will be instructed to mark the number indicating his or her current pain intensity. Below is pain scale format.

No pain	0	1	2	3	4	5	6	7	8	9	10	Worst possible pain
------------	---	---	---	---	---	---	---	---	---	---	----	---------------------

The Participant is to record pain intensity (NRS) at baseline (i.e., pre-dose). Thereafter, the Participant is to record NRS pain intensity assessment at the following time points during the 24 hours period after baseline:

0.5, 1, 1.5, 2, 3, 4, 5, 6, 7, 8, 9, 10, 11, 12, 14, 16, 18, 20, 22 and 24 hours post-dose, and immediately before each use of rescue analgesia.

Ι	Nominal Ti (hours)
0	0
1	0.5
2	1
3	1.5
4	2
5	3
6	4
7	5
8	6
9	7
10	8
11	9
12	10
13	11
14	12
15	14
16	16
17	18
18	20
19	22
20	24

Private and Confidential Study No 22093 Date: MAR 11, 2024

Pain Intensity Difference:

Pain intensity difference (PID) is to be calculated by subtracting the pain intensity at the post-dose time point from the pain intensity at baseline.

$$PID_i = PI_0 - PI_i$$
; for all i > 0.

Where, PI_0 pain intensity at baseline, PI_i is the PI score at post-dose time point i.

Summed Pain Intensity Difference (SPID):

The summed pain intensity difference (SPID) is to be calculated by multiplying the PID score at each post dose time point by the duration (in hours) since the preceding time point and then summing the values over the relevant time period.

$$SPID_{0-2} = \sum_{i=1}^{4} (T_i - T_{i-1}) * PID_i$$

$$SPID_{0-4} = \sum_{i=1}^{6} (T_i - T_{i-1}) * PID_i$$

$$SPID_{0-6} = \sum_{i=1}^{8} (T_i - T_{i-1}) * PID_i$$

$$SPID_{0-8} = \sum_{i=1}^{10} (T_i - T_{i-1}) * PID_i$$

$$SPID_{6-12} = \sum_{i=8}^{14} (T_i - T_{i-1}) * PID_i$$

$$SPID_{0-12} = \sum_{i=14}^{14} (T_i - T_{i-1}) * PID_i$$

$$SPID_{12-16} = \sum_{i=14}^{16} (T_i - T_{i-1}) * PID_i$$

$$SPID_{16-20} = \sum_{i=16}^{18} (T_i - T_{i-1}) * PID_i$$

CONFIDENTIAL

$$SPID_{12-24} = \sum_{i=14}^{20} (T_i - T_{i-1}) * PID_i$$
$$SPID_{16-24} = \sum_{i=16}^{24} (T_i - T_{i-1}) * PID_i$$
$$SPID_{0-24} = \sum_{i=1}^{20} (T_i - T_{i-1}) * PID_i$$

Where, $T_0=0$, T_i is actual post-dose time, PID_i is the PID score at post-dose time T_i for all i > 0.

The durations between two time points will be calculated using the actual post-dose times of the pain score measurement. If the actual time is missing, then the nominal planned time will be used.

Pain Relief:

Participants will assess their current pain relief using a 5-point scale as 0: No relief, 1: A little relief, 2: Some Relief, 3: A Lot of Relief, 4: Complete relief (categorical scale). Each Participant will be instructed to mark the number indicating his or her current pain relief.

The Participant is to record pain relief (5-point categorical rating scale) at given time points during the 24-hour period and immediately before first use of rescue medication.

Total Pain Relief (TOTPAR):

Total pain relief (TOTPAR) is calculated by multiplying the pain relief score at each time point by the duration (in hours) since the preceding time point and then summing these over the relevant period.

$$TOTPAR_{0-2} = \sum_{i=1}^{4} (T_i - T_{i-1}) * PAR_i$$
$$TOTPAR_{0-4} = \sum_{i=1}^{6} (T_i - T_{i-1}) * PAR_i$$
$$TOTPAR_{0-6} = \sum_{i=1}^{8} (T_i - T_{i-1}) * PAR_i$$
$$TOTPAR_{0-8} = \sum_{i=1}^{10} (T_i - T_{i-1}) * PAR_i$$

Private and Confidential Study No 22093 Date: MAR 11, 2024

$$TOTPAR_{6-12} = \sum_{i=8}^{14} (T_i - T_{i-1}) * PAR_i$$
$$TOTPAR_{0-12} = \sum_{i=1}^{14} (T_i - T_{i-1}) * PAR_i$$
$$TOTPAR_{12-16} = \sum_{i=14}^{16} (T_i - T_{i-1}) * PAR_i$$
$$TOTPAR_{16-20} = \sum_{i=16}^{18} (T_i - T_{i-1}) * PAR_i$$
$$TOTPAR_{12-24} = \sum_{i=14}^{20} (T_i - T_{i-1}) * PAR_i$$
$$TOTPAR_{16-24} = \sum_{i=16}^{24} (T_i - T_{i-1}) * PAR_i$$

Where, $T_0=0$, T_i is actual post-dose time, PAR_i is the Pain Relief score at post-dose time T_i for all i > 0.

Peak Pain Relief:

Peak pain relief is the highest observed value of pain relief experienced during post-dose assessments of the study.

Peak Pain Intensity Difference (Peak PID):

Peak pain intensity difference is the highest observed value of pain intensity difference calculated by formula given above in this section.

Time to first Perceptible Relief:

Time to first perceptible relief is the time when the Participant experiences any perceptible pain relief after administration of study drug and stops the first stopwatch. If it is not stopped, time will be censored at the time of last pain relief score assessment or at the first use of rescue medication, whichever comes first.

Time to meaningful relief:

Time to meaningful relief is the time when the Participant experiences relief that is meaningful after the administration of study drug and stops the second stopwatch. If it is not stopped, time will be censored at the time of last pain relief score assessment or at the first use of rescue medication, whichever comes first.

Time to first perceptible relief confirmed by meaningful relief:

Time to first perceptible relief confirmed by meaningful relief is defined as the time to perceptible pain relief (the first stopwatch time) for those Participants who had confirmed meaningful pain relief immediately after first stopwatch and it will be time to meaningful pain relief (the second stopwatch time) for those Participants who did not confirm the meaningful relief before second stopwatch. If stopwatch is not stopped, time will be censored at the time of last pain relief score assessment or at the first use of rescue medication, whichever comes first.

Time to the First Use of Rescue Medication:

Time to first use of rescue medication for pain is defined as the time from first study drug administration to the first use of rescue medication. If rescue medication for pain is not taken, the time will be censored at the time of the last pain intensity score assessment.

Time to achieve complete pain relief:

Time to achieve complete pain relief is defined as the time from first study drug administration to the achieve complete pain relief. If complete pain relief not achieved, the time will be censored at the time of the last pain relief score assessment.

Cumulative proportion of Participants taking rescue medication:

The cumulative proportion of Participants taking rescue medication will be calculated as the cumulative number of Participants who taken rescue medication by a given timepoint divided by the number of Participants treated in respective treatment group.

Participants with 'at least a 2-point PID':

Participants with observed PID score greater than or equal to 2 at any post dose timepoints will be considered as 'at least a 2-point PID'. The same previous formula will be used to calculate the Pain intensity difference (PID).

Participant's Global Assessment of Investigational Product:

At hour 24 or immediately prior to the first dose of rescue medication (if prior to hour 24), study participants will be asked to provide a Global Assessment of investigational product after completion of the other assessments. The Participant will be instructed to score his or her global evaluation of the study treatment on a 5-point categorical scale.

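### SAP 4.1 starts every SPID and TOTPAR window that does not begin at hour 0 one index too early, so ten secondary endpoints cover the wrong hours

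*SAP*

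**What the plan says.** SAP section 4.1 gives a table that pairs an index i, from 0 to 20, with a column headed "Nominal Ti (hours)". In it, i=8 is 6 h, i=14 is 12 h, i=16 is 16 h and the last row, i=20, is 24 h. In words, SPID is obtained by "multiplying the PID score at each post dose time point by the duration (in hours) since the preceding time point" and adding up over the window. TOTPAR follows the same rule with pain relief scores.

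The formulas for windows that do not start at dosing are printed as:

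- "SPID_{6-12} = \sum_{i=8}^{14} (T_i - T_{i-1}) * PID_i"
- "SPID_{12-16} = \sum_{i=14}^{16} (T_i - T_{i-1}) * PID_i"
- "SPID_{16-20} = \sum_{i=16}^{18} (T_i - T_{i-1}) * PID_i"
- "SPID_{12-24} = \sum_{i=14}^{20} (T_i - T_{i-1}) * PID_i"
- "SPID_{16-24} = \sum_{i=16}^{24} (T_i - T_{i-1}) * PID_i"

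The five matching TOTPAR formulas use the same limits, for example "TOTPAR_{16-20} = \sum_{i=16}^{18} (T_i - T_{i-1}) * PAR_i". SAP 7.7.2 sends the analysis of the secondary SPID and TOTPAR endpoints back to these formulas. Protocol 9.4.1 states the weighting rule in words only and gives no index limits.

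**The concern.** Each product (T_i − T_{i−1}) × score_i belongs to the interval that ends at T_i. A window opening at hour s should therefore begin with the index after the one whose time is s. The SAP begins with the index for s itself, so each sum takes in one whole interval that lies before the window.

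All ten endpoints are listed in SAP 5.2. Under SAP 7.7.2 each is reported with LS means, differences, confidence intervals and pairwise p-values. If the formulas are coded as printed, those results describe hours that differ from their labels. Adjacent windows also share an interval, so the parts no longer add up to the whole. In the 16-20 h window, the interval pulled in is 14-16 h, where effect left over from earlier is counted as late effect. The two 16-24 formulas cannot be run literally at all, because they call for indices 21 to 24.

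**Working it through.** **Inputs (index table, SAP 4.1).** T_0=0, T_4=2, T_6=4, T_7=5, T_8=6, T_10=8, T_13=11, T_14=12, T_15=14, T_16=16, T_17=18, T_18=20, T_19=22, T_20=24 h. The last index is 20.

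**Formula.** The hours covered by a sum from i=a to i=b telescope:

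Σ(T_i − T_{i−1}) = T_b − T_{a−1}, running from T_{a−1} to T_b.

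**Control: windows that start at 0 (a=1, T_{a−1}=0).**

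- 0-2: T_4 − T_0 = 2 h
- 0-4: T_6 − T_0 = 4 h
- 0-6: T_8 − T_0 = 6 h
- 0-8 (primary): T_10 − T_0 = 8 h
- SPID0-24: T_20 − T_0 = 24 h
- TOTPAR0-12: T_14 − T_0 = 12 h

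All of these match their labels, which confirms this reading of the table and rule.

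**Windows that start later, with the limits as printed (same for SPID and TOTPAR).**

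| Window | Printed i | T_b − T_{a−1} | Hours covered | Hours named | Excess |
|---|---|---|---|---|---|
| 6-12 | 8 to 14 | 12 − 5 = 7 | 5-12 | 6 | 1/6 = 16.7% |
| 12-16 | 14 to 16 | 16 − 11 = 5 | 11-16 | 4 | 1/4 = 25% |
| 16-20 | 16 to 18 | 20 − 14 = 6 | 14-20 | 4 | 2/4 = 50% |
| 12-24 | 14 to 20 | 24 − 11 = 13 | 11-24 | 12 | 1/12 = 8.3% |
| 16-24 | 16 to 24 | 24 − 14 = 10 (upper limit cut to 20) | 14-24 | 8 | 2/8 = 25% |

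The 16-24 row holds only if the non-existent indices 21 to 24 are ignored. Read strictly, that sum is undefined.

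**Additivity.** The i=8 term (5-6 h) is in both 0-6 and 6-12, so together they carry 6 + 7 = 13 h of weight for a 12 h span. The i=16 term (14-16 h) is in both 12-16 and 16-20, which carry 5 + 6 = 11 h for an 8 h span.

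**Illustration.** This assumes a constant PID of 3, a value not taken from the documents. SPID16-20 would be 6 × 3 = 18 as printed, against 4 × 3 = 12 for the named hours.

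**Actual times.** SAP 4.1 uses actual assessment times. The permitted deviations are 5 minutes up to hour 8 and 8 minutes from hour 9, so they cannot account for an error of 1 to 2 hours.

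**The case against.** The strongest reply is that the intent is clear. The rule in words and the window names are right, and a programmer following them would get the correct hours. The programs and table shells are not in these documents, so it is not known that the printed limits were coded. That is fair, but SAP 7.7.2 names the section 4.1 formula as the method. At best the formula and its label conflict, and two programmers could reach different numbers. A silent correction would itself depart from the SAP, and SAP section 1 requires deviations to be described and justified in the study report.

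Second, the inferential stakes are limited. The fixed testing sequence covers SPID0-8 only, and no confirmatory comparison uses an affected window. The same limits apply to every arm, so the randomised comparison stays valid for a somewhat different window. The percentages measure time weight, not treatment effect. For participants already rescued, the imputation rule makes PID zero or negative, so the extra interval adds nothing positive for them. Duration is also addressed by time to rescue, cumulative rescue use and SPID0-24. All of this stands. It bounds the consequence but does not make the formulas right.

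Third, the text was machine-read from PDF. A reading fault is plausible for two side items: SPID0-12 is printed as i=14 to 14, and no TOTPAR0-24 formula appears. The conclusion rests on neither. For the rest it is not plausible, because the same start-index pattern occurs in ten formulas and the upper limit of 24 occurs in both 16-24 formulas.

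**Conclusion.** Wrong as written, and it should be corrected. The SPID and TOTPAR formulas for 6-12, 12-16, 16-20, 12-24 and 16-24 h each include one interval before the window opens. That adds 1 hour to the windows opening at 6 or 12 h and 2 hours to those opening at 16 h. The two 16-24 formulas also run past the end of the index table.

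This follows from the SAP's own table and weighting rule at nominal times and needs no outside figure. The effect on treatment differences, standard errors or p-values cannot be derived from the documents and is not claimed. The primary endpoint and the sample size are untouched.

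**What to change.** In SAP 4.1, for both SPID and TOTPAR, replace the limits as follows:

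- 6-12: i=9 to 14 (T_14 − T_8 = 12 − 6 = 6 h)
- 12-16: i=15 to 16 (T_16 − T_14 = 16 − 12 = 4 h)
- 16-20: i=17 to 18 (T_18 − T_16 = 20 − 16 = 4 h)
- 12-24: i=15 to 20 (T_20 − T_14 = 24 − 12 = 12 h)
- 16-24: i=17 to 20 (T_20 − T_16 = 24 − 16 = 8 h)

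In the source file, confirm that SPID0-12 runs from i=1 to 14 and that TOTPAR0-24 is defined as i=1 to 20, adding it if it is absent. Check the derivation programs against these limits. A simple test is that, for each participant, 0-6 plus 6-12 equals 0-12, and 12-16 plus 16-24 equals 12-24.

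The cost is an edit to the SAP and the matching program lines. If results have already been produced with the printed limits, rerun the ten endpoints and record the correction in the study report.

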3.1 Handling of Missing Data

3.1.1 Handling of Missing Data for Efficacy Assessments

Use of Rescue Medication:

In all analyses, for participants who take rescue medication, all pain intensity scores after intake of rescue medication will be imputed by the worse of the baseline or the score assessed immediately before taking rescue medication. All pain relief after intake of rescue medication will be imputed by "no relief" (0).

Missing data for efficacy parameter:

If Participants have missing pain data (i.e., pain intensity or pain relief scores) within the 24 hours period for the collection of pain rating data, but nonetheless complete the 24-hour period, then any missing timepoints will be replaced by a time-weighted average of the previous and the next available values (i.e., a linear interpolation for missing values) of the pain data (pain intensity / pain relief score). Intermittent missing data will only be imputed using linear interpolation method and if needed round down to the nearest whole number for pain relief scores, whereas for the categorical pain intensity the value will be rounded up to the nearest whole number.

Interpolation Formula,

$$y = \frac{y_2 - y_1}{x_2 - x_1} (x - x_1) + y_1$$

Where, and if needed round down to the nearest whole number for pain relief scores, whereas for the categorical paint intensity the value will be rounded up to the nearest whole number. y = missing pain data to be imputed, x = respective timepoint of y. y_1 and y_2 = pre and post available pain score of the missing pain data.

 x_1 and x_2 = respective timepoints of y_1 and y_2 .

If Participants do not complete the pain intensity/pain relief assessments for the full 24 hours, then the primary analysis will be calculated up to the last available timepoint, with no imputation for later timepoints.

In a sensitivity analysis, Participants who drop out of the study early because of a related AE or lack of efficacy will have later missing timepoints imputed using a worst-observation-carried-forward (WOCF) method, in which their worst observation at baseline or any time thereafter is imputed. For Participants dropping out early for any other reason, a last-observation-carried-forward (LOCF) imputation will be used.

No imputation will be done for missing data on stopwatch assessments of perceptible and meaningful pain relief. Instead, if data are missing for those assessments, data will be censored as described in Section 4.1.

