The definitions and censoring rules are defined in Section 4.1. Median time will be compared between the treatment groups and placebo using a log-rank test stratified by baseline pain intensity (Categorical pain intensity), pair wise comparison will be made using Tukey-Kramer method and adjusted P-value will be reported. The summary statistics (25th percentile, Median, 75th percentile and it 95% CI) and overall K-M estimates with 95% CI will be presented by treatment groups. The analysis will be performed for the ITT Population.

Pain Intensity Difference (PID) and Pain Relief scores at 0.5, 1, 1.5, 2, 3, 4, 5, 6, 7, 8, 9, 10, 11, 12, 14, (16, 18, 20 if awake), 22 and 24 hours post-dose

The PID at each scheduled time point will be calculated using the formula specified in Section 4.1. Descriptive statistics (n, mean, SD, median, minimum, and maximum) will be presented by treatment groups.

Pain Relief score categories will be presented in the form of frequency counts and percentage by treatment groups and overall. Also, the pain relief score at each scheduled time point will be summarised using descriptive statistics (n, mean, SD, median, minimum, and maximum) by treatment groups. The analysis will be performed for the ITT Population.

A graphical illustration of the time effect curve (Time versus Mean PID / Mean pain relief score) will be presented.

Analysis of Peak Pain Intensity Difference (Peak PID)

The peak PID for each Participant will be identified using the description given in Section 4.1.

The Peak Pain Intensity Difference over the entire study (Peak PID0-24) will be summarized by treatment group using descriptive statistics (n, mean, SD, median, minimum, and maximum) and analyzed using an analysis of covariance (ANCOVA) model, which includes Peak PID0-24 as dependent variable, treatment as main effect and baseline pain intensity (Numerical Rating Score) as the covariate. The least square (LS) mean, standard error (SE) and 95% confidence interval (CI) of LS mean will be reported for each treatment group. In addition, the least square mean difference, SE, 95%

Confidence interval of LS mean difference and p-value for all pairwise treatment group (include placebo) comparisons will be reported. The analysis will be performed for the ITT Population.

Analysis of Peak Pain Relief

The peak pain relief for each Participant will be identified using the description given in Section 4.1.

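### Stopwatch onset times are censored at first rescue as if rescue were uninformative, so the Kaplan-Meier curves, upper quartiles and some medians overstate relief

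*SAP*

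**What the plan says.** SAP 4.1 defines time to first perceptible relief, time to meaningful relief, and time to perceptible relief confirmed by meaningful relief. For the first two, the rule for a watch that the participant leaves running is: "time will be censored at the time of last pain relief score assessment or at the first use of rescue medication, whichever comes first". The third carries the same rule: "If stopwatch is not stopped, time will be censored at the time of last pain relief score assessment" or at first rescue if that is earlier. SAP 3.1.1 sets these endpoints apart from the score-based ones: "No imputation will be done for missing data on stopwatch assessments of perceptible and meaningful pain relief".

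SAP 7.7.2 analyses all three in the ITT population by Kaplan-Meier (median and quartiles with 95% CI, overall estimates) and a "log-rank test stratified by baseline pain intensity (Categorical pain intensity), pair wise comparison will be made using Tukey-Kramer method". It plans no competing-risk or rescue-as-failure analysis.

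Rescue is handled differently elsewhere:
- Score endpoints (SAP 3.1.1, stated for all analyses): "all pain intensity scores after intake of rescue medication will be imputed by the worse of the baseline or the score assessed immediately before" rescue, and "All pain relief after intake of rescue medication will be imputed by" no relief, scored 0.
- Time to complete relief (SAP 4.1): "If complete pain relief not achieved, the time will be censored at the time of the last pain relief score assessment".
- Time to first rescue (SAP 4.1): rescue is the event. "If rescue medication for pain is not taken, the time will be censored at the time of the last pain intensity score assessment".

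Protocol 9.4.1 has the stopwatch times analysed in the same way as time to first rescue, where participants without the event are censored at the last assessment. It mentions no censoring at rescue for the stopwatches. SAP 7.13 reports no changes from the protocol. Protocol 6.5.1 has any running watch stopped at rescue and its time recorded on the case report form.

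**The concern.** Kaplan-Meier assumes that a censored participant has the same later chance of the event as those still at risk. Under Protocol 6.5.1 rescue is taken when relief is inadequate or pain returns. A participant who takes rescue before stopping the watch has not had the relief the endpoint measures, and is less likely than the others to have been about to get it. Censoring there redistributes that participant's probability to participants who are doing better.

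The onset medians, quartiles and curves could then describe a better experience than treated participants had. Where rescue is commoner in the comparator, differences between arms would usually be narrowed. The report would also hold two families of relief-time endpoints that follow opposite rescue rules.

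**Working it through.** **1. The plan's own figure.** The only design calculation is for SPID0-8 (Protocol 9.2, SAP 2.3): difference 6.5, SD 16.9, 90% power, alpha 0.05. Two-sided normal formula: n = 2 × (1.960 + 1.282)² × 16.9²/6.5² ≈ 142; the t-based calculation gives 143 per arm, against 144 stated. Power at 144 is 90.4%, and 528/0.95 = 556. It reproduces. No relief rate, rescue rate or power is stated for the stopwatch endpoints, so every rate below is an assumption.

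**2. Rescue before the event, endpoint by endpoint.**

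| Endpoint | Effect of rescue |
|---|---|
| SPID, TOTPAR | counted as failure (SAP 3.1.1) |
| Time to complete relief | stays at risk as not relieved: censored at last relief assessment, with post-rescue relief scored 0 |
| Time to first rescue | is the event |
| Three stopwatch times | censored, treated as uninformative |
| Peak PID, peak relief, 2-point PID | observed values; no rescue rule in the definition |
| Global assessment | rated just before first rescue |

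For SPID and TOTPAR, this takes the SAP 3.1.1 rescue rule as governing despite the no-imputation label in SAP 7.7.1 to 7.7.3. For time to complete relief, the entry is inferred from SAP 3.1.1, because the definition itself does not mention rescue.

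**3. Constant hazards.** Let relief occur at rate a and rescue at rate b per hour.
- Kaplan-Meier censored at rescue estimates 1 − exp(−a·t).
- The share of treated participants relieved before rescue is a/(a+b) × [1 − exp(−(a+b)·t)].

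Example with a + b = 0.35 and a = 0.105: at 24 h, 1 − exp(−2.52) = 92%, against 0.30 × [1 − exp(−8.4)] = 30%.

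| Actual relief at 24 h | Kaplan-Meier at 24 h | Excess at 24 h | Excess at 2 h |
|---|---|---|---|
| 30% | 92% | +62 | +3.8 |
| 50% | 98.5% | +49 | +4.4 |
| 70% | 99.7% | +30 | +3.5 |
| 80% | 99.9% | +20 | +2.6 |
| 90% | 99.9% | +10 | +1.4 |

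The small 2 h excess belongs to this combined rate. With a = b = 0.30, the 2 h figures are 1 − exp(−0.6) = 45.1% and 0.5 × [1 − exp(−1.2)] = 34.9%, an excess of 10 points.

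**4. Responders and non-responders mixed.** Lognormal relief times in responders (log-SD 0.7 for median 0.5 h, 0.8 for median 1 h). Rescue follows a fixed delay plus an exponential time with mean 1.5 h, and comes 6 h later in responders. Excess at 24 h, in points:

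| Actual relief | Relief median 0.5 h, rescue from 1 h | Relief median 1 h, rescue from 2 h | Relief median 1 h, rescue from 1 h |
|---|---|---|---|
| 30% | +3 | +17 | +30 |
| 50% | +5 | +24 | +33 |
| 70% | +5 | +19 | +25 |
| 85% | +6 | +13 | +14 |

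**5. Medians and upper quartiles.** Lognormal relief (log-SD 0.6); rescue median 2 h in non-responders and 6 h in responders (log-SD 0.5).
- Combination-like arm (20% never relieved, relief median 0.95 h): median 1.14 h under the SAP rule and 1.15 h with rescue as failure; upper quartile about 2.0 and 2.4 h.
- Naproxen-like arm (35%, 1.0 h): median 1.47 and about 1.55 h.
- Placebo-like arm (60%, 1.0 h): median about 3.5 h and not reached.

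If nobody takes rescue before 2 h, the combination and naproxen medians do not change at all.

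Constant hazards with relief 0.30/h in both arms and rescue 0.10 v 0.30/h: the Kaplan-Meier median is ln 2/0.30 = 2.31 h in both. With rescue as failure it is ln 3/0.40 = 2.75 h in the first arm and not reached in the second.

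**6. Log-rank power** (two-sided 0.05, unstratified, no Tukey-Kramer adjustment):

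| Setting | SAP rule | Rescue as failure |
|---|---|---|
| 144 v 48; relief 0.30 v 0.30/h, rescue 0.10 v 0.30/h | 5.5% | 72% |
| 144 v 48; relief 0.35 v 0.20/h, rescue 0.10 v 0.30/h | 63% | 99% |
| 144 v 144; relief 0.35 v 0.30/h, rescue 0.10 v 0.13/h | 20% | 35% |
| 144 v 144; 20% v 35% never relieved, relief median 0.95 v 1.0 h | 76% | 82% |

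**The case against.** The strongest defence is that this is a choice of estimand. Censoring at rescue gives a valid log-rank comparison of relief hazards before rescue, and rescue has its own endpoints. That stands for the test. In the first power setting the relief hazards are equal, so 5.5% is the correct behaviour of an onset test and the 72% comes entirely from rescue. The defence does not cover the reported medians, quartiles and curves, which will be read as describing all treated participants.

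A second defence is that Protocol 6.5.1 stops the watches at rescue, so observation ends there. But a participant rescued without relief is known to have had none up to that time, and later relief could not be credited to study drug alone. Such a participant can be carried to 24 h as not relieved without new data.

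Third, the protocol's instruction to analyse these times similarly leaves detail to the SAP. That is fair, but its only stated censoring point is the last assessment, so adding rescue belongs in SAP 7.13.

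A reader might also infer more than the documents support:
- *That every other endpoint counts rescue as failure.* Peak PID, peak relief, 2-point PID and the global assessment have no such rule in their definitions.
- *That the excess is always largest in the arm that fails most.* In step 4 it peaks at 50% actual relief when the relief median is 1 h, and with early relief it is smallest at 30%. With no relief events it is zero.
- *That the combination is favoured.* Where rescue is commoner in the comparator, the usual effect is to narrow the difference.

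**Conclusion.** The point holds for estimation. Censoring at rescue is informative, and one minus Kaplan-Meier overstates the share of treated participants who got relief. The rule is also inconsistent with SPID and TOTPAR, with time to complete relief, and with the plain reading of Protocol 9.4.1.

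The size cannot be fixed from the documents. Over the assumed rates the excess is about 3 to 62 points at 24 h. At 2 h it is 1 to 4 points for a combined rate of 0.35/h, and 10 in one faster setting. The distortion lies mainly in the later curves, upper quartiles and medians of arms with much rescue, such as placebo. Combination and naproxen medians changed by less than 0.1 h in the mixture settings of step 5. It is often, but not always, larger where rescue is more frequent.

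These endpoints are secondary and outside the SPID0-8 testing sequence. The primary conclusion and the sample size do not change.

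**What to change.** In SAP 4.1 and 7.7.2, for all three stopwatch endpoints:
1. Keep a participant rescued without relief at risk to 24 h as not relieved, even if that participant later leaves the study. Alternatively, report cumulative incidence with rescue as a competing event and compare arms by Gray's test.
2. Censor participants who drop out without relief or rescue at their last assessment.
3. Keep the present rule as a sensitivity analysis, described as relief hazard before rescue.
4. State that a watch stopped because of rescue (Protocol 6.5.1) is not a relief event. The present SAP wording, which applies only when the watch is not stopped, could let a rescue stop pass as relief. Confirm that the case report form separates the two.
5. Record the choice in SAP 7.13.

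The cost is SAP wording and a small change to the derivation; the censoring change needs no new data. The downside is that the endpoint becomes relief without rescue, which combines onset with rescue avoidance, and placebo medians may not be reached.
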